Methamphetamine (MA) addiction is a chronic relapsing conditions that causes devastating physical and psychiatric harm to affected individuals [1]. These include increased risk of psychosis [2], depression/anxiety [1], suicidal behavior [3], completed suicide [4], and even all-cause mortality when compared to users of cocaine, alcohol or cannabis [5]. However, since discontinuation of MA use leads to negative emotional states, abstinence from MA poses intense difficulty for dependent individuals. Given these observations, basic and clinical research studies have focused on the development of new pharmacological interventions [6], but have not led to Food and Drug Administration (FDA) approved pharmacotherapies that improve cognitive deficits and depressive symptoms during MA discontinuation [7].

Methamphetamine has deleterious effects on dopaminergic brain systems [8], and prolonged amphetamine exposure is associated with Parkinson's disease [9]. Animal studies suggest that MA use predisposes to Parkinson's via degeneration of the midbrain dopaminergic neurons that project to striatum [10]. A recent epidemiologic study found a significant correlation between the development of Parkinson's disease (165% higher risk) in MA users followed for up to 10 years [11]. This finding was replicated in a larger sample of MA users (n=40,472) versus an appendicitis group (n=207,831; hazard ratio=1.76), and even a cocaine group (n=35,335; hazard ratio=2.44) [12].

Converging evidence implicates mitochondrial dysfunction in MA toxicity [8, 13-15]. Mitochondrial pathways interact to cause MA-induced neuronal apoptosis and death [16]. MA inhibits enzyme complexes of the electron transport chain, resulting in dopaminergic neurotoxicity because electron transport chain inhibitors increase reactive species [17-19]. Inhibition of complex I activity by MA [16] also decreases ATP production. MA produces mitochondrial fragmentation in progenitor cells [20], releasing apoptogenic molecules from mitochondria [21].

Brain Phosphocreatine (PCr) Levels and Glutamate Excitotoxicity in Methamphetamine Use:

A key phosphorus (^{31}P) magnetic resonance spectroscopy (MRS) finding from our ongoing research is significantly decreased phosphocreatine (PCr) in MA users, an effect that is greater in females than males [22]. Notably, in rats creatine administration significantly increases the brain content of both creatine and PCr [23]. In human studies, the increase in brain total creatine (PCr + creatine) after oral creatine supplementation is a finding replicated by three independent groups, including ours [24-26].

The importance of assessing glutamatergic systems in MA users is attested to by the fact that more than 80% of neurons are excitatory, and that greater than 90% of synapses release glutamate [27]. Of relevance to our preliminary proton (^1H) MRS findings showing an association between the glutamine/glutamate ratio and lifetime MA use, it has been reported that PCr stimulates synaptic glutamate uptake thereby reducing extracellular glutamate [28], which is another potential neuroprotective mechanism of creatine. Importantly, depletion of PCr and ATP is an early event in glutamate excitotoxic neurodegeneration [29, 30]. Therefore, based on our finding of decreased PCr in MA users, it is of interest that a recent ^1H -MRS investigation reported that glutamate levels in frontal white matter are significantly higher in abstinent MA users versus control subjects [31], which is compatible with MA-induced neurotoxicity.

Female Methamphetamine Initiation, Addiction and Relapse are Influenced by Depression:

The prevalence of pre-morbid depressive disorders in MA users is high, with a majority reporting a significant lifetime history of depression [1, 3, 70]. For example in one study [70], MA users had a 62% rate of depression and a 23% rate of suicidality prior to MA use. After MA was initiated, the rate of depression increased to 79% [70]. Studies reporting gender differences in psychopathology have found that MA use is associated with depression in both adult [60] and

adolescent [71] females. In one study, depressive symptoms were endorsed on the Addiction Severity Index (ASI) by 68% of female MA users [3]. In another, early-onset MA use in females was significantly associated with premorbid depressive disorders, while the same was *not* true for males [72]. Female MA users with depression are less likely to be employed, more likely to use MA to manage their mood, use more grams of MA per 30-day period, use MA more times per day on more consecutive days, and are more likely to be binge users [73]. The diagnosis and treatment of depression and anxiety in MA users is complicated by the fact that withdrawal-associated dysphoria is persistent, and may be the result of *MA-induced neurotoxicity* [74]. Therefore, an ideal intervention for depression and anxiety in the setting of MA addiction would be one that targeted *both* neurotoxicity and negative emotional states.

Research has shown that females may respond better to treatment of MA use disorders than males [60, 75]. In fact, patient gender predicts both treatment engagement and abstinence during rehabilitation [76], a gender difference *not* found in cocaine- or alcohol-dependent research samples [77]. As a result, the recommendation has been made to take gender into account in developing treatments for MA use disorders [60, 75].

Creatine is a Novel Strategy for Cognitive Enhancement and Neuronal Repair in MA Addiction:

Our preliminary data, combined with the extant literature, suggest that creatine administration is a safe, hypothesis-driven strategy for: (a) Increasing brain PCr, NAA and GABA levels, thus providing neuroprotection and neuronal repair; (b) Reducing both depression and anxiety symptoms; and (c) Improving cognitive deficits in female MA users. Based on evolving understanding of MA neurotoxicity, a novel therapeutic strategy that has been suggested is to utilize cognitive enhancement and neuronal repair as pharmacotherapy targets in stimulant addiction [56, 57]. This stems, in part, from the fact that solely addressing the drug's addictive properties may be insufficient to address the diverse neuropathological injuries caused by MA [15]. However, in the absence of approved medications for MA use disorders, an initial step toward pursuing this innovative strategy is to assess the clinical and translational impact of a neuroprotective agent such as creatine in MA users.

Summary Significance and Relevance for This Proposal:

The lack of safe and effective pharmacological treatments for MA use disorders is a critical barrier to improved treatment outcomes. This proposal builds on the published translational findings of reduced PCr[22] and NAA [34, 124] levels in MA use disorders, and the clinical and neuroimaging findings from our preliminary study of creatine for MA-using females. At the same time, it follows the recommendation of experts – including NIDA Director [name] and the eminent substance abuse researcher [name] – that strategies outside the brain dopamine reward system be adopted [56, 125, 126]. Achievement of these *Specific Aims* would validate the notion of neuroprotective agents as potential treatments for MA addiction [15], and in particular those which are also capable of improving mood/anxiety and cognitive symptoms. Incorporating pre- and post-treatment imaging into studies of substance misuse can facilitate identification of the neural predictors and correlates of effective MA treatment [127]. Because the effects of drug use on brain function impede patients' ability to benefit from treatment, studies of drug-related alterations in neurobiology utilizing translational study designs are warranted [127]. Thus, we propose an 8-week, randomized, placebo-controlled trial of creatine for females with MA addiction.

Specific Aims for this proposal are: **1. To define the extent of restoration in bioenergetic dysfunction and neuronal viability following creatine supplementation in female MA users.** We hypothesize that creatine will be superior to placebo in the degree of improvement in PCr and NAA levels, measured with ^{31}P -MRS and ^1H -MRS. Changes to the glutamine/glutamate ratio and GABA will be assessed in an exploratory manner. **2. To assess creatine's antidepressant/anxiolytic effect in female MA users.** We hypothesize that creatine will be

superior to placebo in reducing Hamilton Depression Rating Scale (HAMD) and Beck Anxiety Inventory [97] scores. 3. To Measure the Degree of Cognitive Improvement Associated with Creatine in Female MA Users. We hypothesize that creatine will be associated with greater improvement in cognitive function tests, compared with placebo. In addition to these Specific Aims, we will examine urine drug testing results in an exploratory manner, to determine whether creatine vs. placebo is associated with a greater number of MA-free tests

In addition to these **Specific Aims**, we will monitor subjects' MA use, as improvements in brain bioenergetics, mood/anxiety and may decrease MA usage. Therefore, we will record urine drug testing results, to determine whether creatine vs. placebo is associated with a greater number of MA-free tests during the 8 weeks of randomized treatment.

PARTICIPANT SELECTION CRITERIA

123 women will be randomly assigned in a 1:1 ratio to either creatine or placebo for eight weeks. Table 1 outlines eligibility criteria.

TABLE 1 INCLUSION AND EXCLUSION CRITERIA

INCLUSION CRITERIA:

- Female gender, ages 18-55 inclusive
- Current primary diagnosis of MA dependence or abuse, with MA preferred drug of abuse (Lifetime MA use > 20 grams)
- Current diagnosis of Major Depressive Disorder (MDD)
- Current HAMD score ≥ 10
- Clinical Global Impressions–Severity (CGI-S) depression score ≥ 4
- If taking a psychotropic medication for depressed mood, regimen must be stable for ≥ 4 weeks prior to randomization

EXCLUSION CRITERIA:

- Persons unable to provide adequate informed consent
- Persons who are at clinically significant suicidal or homicidal risk
- Primary substance-related diagnosis *other than* MA dependence or abuse
- Comorbid substance dependence diagnosis, other than nicotine (substance abuse diagnoses are not excluded)
- Positive pregnancy test, due to the unknown effects of MRI scanning on the unborn fetus
- Positive test for antibody to the Human Immunodeficiency Virus (HIV)
- History of renal disease
- Clinically significant medical or neurological illness identified by history, physical exam and laboratory testing
- Known or suspected intellectual disability, or developmental disorder, e.g. autism
- History of hypersensitivity reaction to creatine

WITHDRAWAL / EARLY TERMINATION CRITERIA:

- Withdrawal of informed consent
- Suicide attempt
- Psychiatric hospitalization
- Onset of bipolar disorder or psychotic disorder
- Positive pregnancy test
- Incarceration
- Inability to comply with study protocol

▪ Treatment with electroconvulsive therapy (ECT)▪ Increase in HAMD score > 25% from baseline▪ Serious adverse event

▪ HEALTHY CONTROL SUBJECTS:
 
▪ Female gender, ages 18-55 inclusive▪ No current or past DSM-5 diagnosis, as determined by clinical and structured interviews▪ No first-degree relatives with known or suspected DSM-5 diagnosis

DESIGN

The proposed study will use a randomized, double-blind, placebo-controlled design. 123 participants will be randomly assigned in a 1:1 ratio to placebo or 5 grams of daily creatine treatment for eight weeks. We also plan to recruit 24 age-matched females (18-55).

STUDY PROCEDURES

All procedures performed by study personnel are research-related. None of the study activities will be considered standard of care. There will be no cost to study subjects for their participation. Participants will be compensated for their time and travel. Table 2A and 2B outlines the schedule of study procedures for treated participants and healthy controls.

Consent will be obtained before any study procedures are initiated. Potential participants will be informed of the study and offered a consent form to review. They will be encouraged to discuss study participation with their relatives. If a potential participant expresses interest in study participation, the informed consent process will be conducted. After the informed consent process, individuals will be offered time to consider study participation and to ask questions. Subjects and parents/guardians will have the opportunity to discuss the study with a study team member in a setting free of coercion. The language of the informed consent form is written at a level easily understood by the subject and any questions asked by the subject will be answered honestly and free of bias. A specific meeting time will be set up between a study team member and the participant where the entire informed consent document will be carefully explained in its entirety. The length of the meeting will be designed so there is the necessary amount of time for all questions to be answered.

Randomization of participants to the two treatment conditions will take place according to a randomization list generated prior to the start of recruitment. 47 (50%) will be randomized to placebo. The study will be conducted as a double-blind trial, with neither participants nor research staff aware of participant assignment. Except in cases of medical emergency, the double-blind will not be "broken" until recruitment is closed and the final participant has completed 8 weeks of treatment with investigational drug. There is no "washout period" for any participant in this study, and participants randomized to placebo will continue treatment with a psychotropic medication throughout their time in the study.

At the screening visit, an ECG will be conducted in order to examine the heart and ensure participant safety; an adult cardiologist will also evaluate all individuals during the screening phase. If during the MRI/MRS scans we unexpectedly discover something that warrants further inspection, we will refer the participant to her primary care provider for follow-up, along with the MRI/MRS report that shows the findings. Any costs related to following up on unexpected findings will be the responsibility of her and/or her insurance provider. In conjunction with the brain scans performed pre- and post-treatment, a brief battery of cognitive tests will be administered, to evaluate change associated with creatine or placebo. Trained psychometricians administer tests on the day of scanning. Scoring is done blind to subjects' group status, clinical ratings and imaging results. The cognitive testing battery instruments were

chosen because they are sensitive to frontal lobe integrity: the Wisconsin Card Sorting Task (WCST)[129], the Stroop Color-Word Test[130, 131], and the Wechsler Memory Scale (WMS-IV)[132]. Furthermore, the WCST[133], Stroop Test[134] and WMS-IV [90] each have been associated with performance deficits in MA users.

TABLE 2A Schedule of Procedures for Methamphetamine-dependent Females												
	Screening	Treatment Phase								Follow Up Phase		
Study Week →	-2 to 0^a	1*	2*	3*	4*	5*	6*	7*	8*	9	10	11
Informed Consent, Demographics	X											
Medical History & Physical Exam, ECG	X											
Hematology & Chemistries	X									X		
Phlebotomy for Creatinine Levels	X				X					X		
HIV	X											
Pregnancy Test and vital signs	X	X	X	X	X	X	X	X	X	X	X	X
PRISM Diagnostic Interview	X											
ASI	X									X		
Randomization to Creatine or Placebo	X											
Treatment with Creatine or Placebo		X	X	X	X	X	X	X	X			
Urine Drug Screen / Other Drug Use	X	X	X	X	X	X	X	X	X	X	X	X
Concomitant Medications	X	X	X	X	X	X	X	X	X	X	X	X
Food Frequency Questionnaire	X									X		
Cognitive Tests: WCST, STROOP and WMS-IV (with WASI vocabulary)***	X									X		
Adverse Events		X	X	X	X	X	X	X	X	X	X	X
Treatment Program Attendance	X	X	X	X	X	X	X	X	X	X	X	X
Clinical Scales: HAMD**, BAI**, CGI-S**, C-SSRS	X	X	X	X	X	X	X	X	X	X	X	X

³¹ P-MRS and ¹ H-MRS****	X									X		
*During the 8 Treatment Weeks, MA Subjects Have 2 Study Visits Per Week (separated by \geq 48 hours)												
**Procedure will be collected at one of the twice weekly visits												
***MA subjects with difficulty scheduling the cognitive testing appointment may be allowed to omit these measures and continue in the study as to not delay treatment and in order to facilitate timely enrollment, which is critical for this population.												
****If an individual is screened and determined to be a good fit for study participation but also has a contraindication to MRI scanning, the principal investigator may allow them into the study, however, they will not be scanned for their safety.												
CGI-S = Clinical Global Impressions-Severity Depression Score; C-SSRS = Columbia-Suicide Severity Rating Scale; HAMD = Hamilton Rating Scale for Depression; BAI = Beck Anxiety Inventory; PRISM = Psychiatric Research Interview for Substance and Mental Disorders; STROOP = Stroop Color Word Test; WCST = Wisconsin Card Sorting Test; WMS-IV = Wechsler Memory Scale; WASI = Wechsler Abbreviated Scale of Intelligence; ASI = Addiction Severity Index.												
^a Screening may happen over the course of 2-3 visits.												

TABLE 2B Schedule of Procedures for Healthy Controls

	Screening									Final Visit
Study Week →	-1 to 0 ^a	1	2	3	4	5	6	7	8	9
Informed Consent, Demographics	X									
Medical History & Physical Exam, ECG	X									
Hematology & Chemistries	X									
Phlebotomy for Creatinine Levels	X									
HIV	X									
Pregnancy Test	X									X
PRISM Diagnostic Interview	X									
Food Frequency Questionnaire	X									X
Urine Drug Screen / Other Drug Use	X									X
Concomitant Medications	X									X
Vital Signs	X									X
Cognitive Tests: WCST, STROOP and WMS-IV (with WASI vocabulary)	X									X
Treatment Program Attendance	X									X
Clinical Scales: HAMD**, BAI**, CGI-S**, C-SSRS	X									X

³¹ P-MRS and ¹ H-MRS	X									X
CGI-S = Clinical Global Impressions-Severity Depression Score; C-SSRS = Columbia-Suicide Severity Rating Scale; HAMD = Hamilton Rating Scale for Depression; BAI = Beck Anxiety Inventory; PRISM = Psychiatric Research Interview for Substance and Mental Disorders; STROOP = Stroop ColorWord Test; WCST = Wisconsin Card Sorting Test; WMS-IV = Wechsler Memory Scale; WASI = Wechsler Abbreviated Scale of Intelligence.										
^a Screening may happen over the course of 2-3 visits.										

RISKS AND BENEFITS TO STUDY PARTICIPANTS

- During the intake and assessment interview, participants may become emotionally upset when asked about their psychiatric history including suicide attempts, or physical and sexual abuse.
- There is a 50% chance that the participant will be assigned to placebo, in which they will not receive creatine.
- Participants may experience discomfort or swelling when blood is drawn for laboratory tests. Rarely, infection can result from blood draws.
- It is possible that the participant's illness could worsen during the study. This could be related or unrelated to the study. Individuals with Major Depressive Disorder are at risk for depression, suicidal ideation, and suicide attempts as part of their illness. If the participant's illness worsens to the point that the study doctor considers them a danger to themselves or others, they will be hospitalized. If the participant is hospitalized they will be withdrawn from the study. In the event of hospitalization, the participant or the participant's insurance company will be responsible for the associated costs.
- It is possible that treatment with creatine will not be effective for the participant's depression, and that study participation will therefore delay the start of effective treatment.
- The researchers will take precautions to safeguard the participant's confidentiality, but it is possible that a breach of confidentiality could occur. A Certificate of Confidentiality has been obtained for this study.
- The participants may experience gastrointestinal discomfort as a result of taking study medication. We recommend taking the study medication with food to reduce possible stomach discomfort.
- MRI/MRS scans do not use ionizing radiation like x-rays or CT scans. Instead, magnetic fields and radio waves are used to take the pictures. There are no known risks related to MRI scans – other than the risk of injury when metallic objects are brought into the scanning room by mistake. Serious injury can occur during an MRI scan to persons who have:
 - Cardiac (heart) pacemakers.
 - Metal clips on blood vessels (also called stents).
 - Artificial heart valves.
 - Artificial arms, hands, legs, etc.
 - Brain stimulator devices.
 - Implanted drug pumps.
 - Cochlear [6] implants.
 - Ocular [118] implants or known metal fragments in eyes.
 - Exposure to shrapnel or metal fillings
 - Other metallic surgical parts.
 - Orthodontic braces on the teeth.
 - Body jewelry or piercings that cannot be removed for the scan.
 - Certain tattoos with metallic ink (please tell us if your child has a tattoo)
 - Certain transdermal (skin) patches such as NicoDerm (nicotine for tobacco dependence),
 - Transderm Scop (scopolamine for motion sickness), or Ortho Evra (birth control)

If the participants have any such devices, or has had a surgery where metal devices were placed in their body, they cannot take part in the study unless cleared for MRI scanning by the surgeon who implanted the medical device(s) or unless the principal investigator allows the individual to take part in the study without being scanned.

- Serious risks exist if ferromagnetic objects (things that stick to magnets) are brought into the scanning area. These items can become dangerous flying objects, and are not allowed near the MRI scanner.
- The FDA has approved the 3T scanner for routine clinical studies in children. The FDA has decided that MRI machines of 8T or less do not pose a risk. Although the scans we are using in this study have no known risks, there could be ill effects that are delayed, such that they have not yet been recognized by the FDA. The brain scans do not cause pain. Apart from the scanner noise, the participant will not know the scan is taking place.
- Inside the scanner, some people experience claustrophobia (fear of being in small spaces), dizziness, headaches, or a metallic taste in the mouth. Some people experience double vision or see flashing lights. These symptoms are temporary, and will stop when the participant leaves the scanner.
- The participant may feel cramped inside the scanner. There is a mirror placed inside the scanner so that your child can see his or her face, and look out into the scanning room. The technologist will be able to hear the participant at all times.
- Very rarely, someone having an MRI scan feels a tingling in his or her back. This is due to the magnetic field changing quickly during the scan.
- The precautions taken will avoid all the known risks related to MRI scans. The participant can stop the scan at any time.

We cannot promise any benefits to the participants from being in the study. However, there are some possible benefits to the participants if they participate in this study:

- Participants will receive a thorough medical and psychiatric evaluation, and will be followed more closely than in routine clinical care.

Other than direct benefits to the participants, there are possible indirect benefits:

- Results from the study will help doctors understand the way creatine affects MA users with depression, and thus, this could help us improve treatment options.
- The brain scans may improve our understanding of the biology of depression in female MA users. However, that would not directly benefit the participants.
- The participants will receive a copy of the clinical MRI of their brain, if they wish. A copy of the MRI scan report will also go to the research team.

DATA SAFETY MONITORING PLAN

The study team will perform monitoring of the study records on a continuous basis. Co-investigator, [name], will oversee data accuracy and completeness.

- a. *Adverse Events/Serious Adverse Events to the IRB, FDA and NIDA*
 - i. Reporting to the University of Utah Institutional Review Board. Adverse events (AEs) and Serious Adverse Events (SAE) that are unexpected and unrelated will be reported to the University of Utah Institutional Review Board (IRB) with the annual request for study continuation. For AEs/SAEs that are unexpected, related to study participation and place participants at risk will be reported via the IRB's electronic reporting system as soon as possible after the PI learns of the event, but in all cases within 10 working days.

- ii. Reporting to the Food and Drug Administration. The PI shall notify the Food and Drug Administration (FDA) in a written investigational new drug [118] safety report of any adverse experience associated with the use of the drug that is both serious and unexpected. In each written IND safety report, the investigators shall identify all safety reports previously filed with the IND concerning a similar adverse experience, and shall analyze the significance of the adverse experience in light of the previous, similar reports. Each notification shall be made as soon as possible and in no event later than 15 calendar days after the sponsor's initial receipt of the information. Each written notification may be submitted on FDA Form 3500A or in a narrative format (foreign events may be submitted either on an FDA Form 3500A or, if preferred, on a CIOMS I form; reports from animal or epidemiological studies shall be submitted in a narrative format) and shall bear prominent identification of its contents, i.e., "IND Safety Report." Each written notification to FDA shall be transmitted to the FDA new drug review division in the Center for Drug Evaluation and Research or the product review division in the Center for Biologics Evaluation and Research that has responsibility for review of the IND. If the FDA determines that additional data are needed, the agency may require further data to be submitted.
 - a. The study team will send an annual report 60 days within the "study may proceed" date.
- iii. Reporting to the National Institute on Drug Abuse. The PI will notify the grant program officer by email of SAEs as soon as possible and in no event later than 15 calendar days. Other AEs will be summarized in the annual progress report.

- b. *Reporting IRB Actions to NIDA.* The grant program officer will be made aware of IRB actions via email correspondence from the PI.
- c. *Reporting Protocol Changes.* Changes to the protocol will be submitted to the IRB and FDA for approval before the changes are implemented. Once the IRB and FDA have issued approval of protocol changes, the PI will submit a summary of the protocol changes and the protocol to the grant program officer. The NIDA program officer must agree upon proposed protocol changes before they can be implemented.
- d. *Reporting Protocol Violations/Deviations to the IRB and FDA*
 - i. Reporting to the University of Utah Institutional Review Board. If a protocol violation/deviation meets one or more of the following criteria, the PI will submit the violation/deviation via ERICA within 10 working days from the time the investigator learns of the event.
 - Intended to eliminate apparent immediate hazard to a research participant; or
 - Harmful (caused possible harm to participants or others, or places them at increased risk of harm – including physical, psychological, economic, or social harm, such as breach of confidentiality); or
 - Possible serious or continued noncompliance (such as a deviation that has happened previously and is now being repeated).
 - ii. Reporting to the Food and Drug Administration. Protocol violations/deviations will be summarized in the annual IND report.

Trial Stopping Rules

In our open-label study of 5 grams of daily creatine for 8-weeks, there were no unanticipated problems or SAEs reported. Considering this is a feasibility study of double-blind, placebo-controlled creatine at the same dose as our open-label study, and the open-label creatine was well tolerated with a low side effect profile, we have not adopted rules for stopping the study. We have, however, developed criteria for early termination of participants and the criteria are listed below:

- Suicide attempt
- Psychiatric hospitalization

- Onset of bipolar disorder or psychotic disorder
- Positive pregnancy test
- Incarceration
- Inability to comply with the study protocol

IMAGING METHODS AND DATA ANALYSIS

1. Neuroimaging Protocol

i. Magnetic Resonance Imaging (Siemens Trio 3T MRI system)

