Overall Analytic Strategy: The analyses proposed are generalized estimating equations (GEE) regression modeling, which will be used for our longitudinal data analyses with group comparison across treatment visits for the variables of metabolite levels, depression/anxiety symptoms, and cognitive tests. GEE allows robust estimations of standard errors and permits adjustment for time-varying covariates. We assume that measurements made closer in time are more correlated than those made farther apart. Thus, first-order autoregressive structure is assumed. For our repeated measurement data, GEE fits a population-averaged model with working correlation structure to statistically evaluate the time effect of creatine supplementation. We will control for age, other drug abuse, anxiety scores, and tissue partial volume effects in each GEE model. Sidak multiple comparison procedure will be employed to adjust for family wise error (FWE) rate. The Sidak tests make conservative controls of FWE, giving slightly smaller adjusted p-values than the Bonferroni correction.

Overall Power and Sample Size Calculations: For this pilot study, considering a 20% attrition rate, 95 participants will be recruited to achieve a sample size of 75. To determine the minimum effect that would likely be detected with a sample size of 75, a power analysis was performed. Effect for the power analysis was specified as average baseline (over two measures) HAM-D scores compared with average HAM-D scores during active treatment (over eight measures). A gradual onset of effect during active treatment is assumed, starting with an effect of 0 and ending with an effect of 0.5, resulting in an average effect during treatment of 0.25. The effect to be tested was treated as a linear combination of the separate measures (y^*), and a pattern of correlation of 0.5 was used. This generated a standard deviation [105] for y^* that will be different from the within-occasion SD for Y itself. Then the effect magnitude specified was divided by the $SD(y^*)$ to generate an "effective" or de facto effect size, which resulted in an effect size of 1.09 with a power of 0.87.

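### The exploratory MA-use comparison is worded as a number of MA-free urine tests with no denominator or missed-test rule, so a difference in retention between arms can look like a difference in MA use

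*Combined protocol and SAP*

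**What the plan says.** The text following the Specific Aims says urine results will be recorded "to determine whether creatine vs. placebo is associated with a greater number of MA-free tests during the 8 weeks of randomized treatment". The Specific Aims paragraph sets the status of this comparison: "we will examine urine drug testing results in an exploratory manner".

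Table 2A has a row for "Urine Drug Screen / Other Drug Use" with a mark in every treatment week, and its footnote states "During the 8 Treatment Weeks, MA Subjects Have 2 Study Visits Per Week". The HAMD, BAI and CGI-S carry a mark limiting them to one of the two weekly visits. The urine row carries no such mark.

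The withdrawal criteria in Table 1 include suicide attempt, psychiatric hospitalization, incarceration, a HAMD rise above 25% and "Inability to comply with study protocol". No provision is made for urine testing after withdrawal. The power section plans for overall attrition only: "considering a 20% attrition rate, 95 participants will be recruited to achieve a sample size of 75".

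The Overall Analytic Strategy lists metabolites, depression and anxiety symptoms, and cognitive tests as the GEE outcomes, and does not name urine results. The data-management section provides a code for missing entries but no analysis rule for a missed urine test.

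**The concern.** A count of MA-free tests cannot exceed the number of tests given. Without a denominator, a missed test lowers the score exactly as a positive one does. A woman withdrawn after week 3 with six negatives out of six scores 6. A completer with seven negatives out of 16 scores 7 and ranks better. The count mixes abstinence with time in the trial.

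That matters between arms only if retention or attendance differs, and the plan contains routes by which it could. Several withdrawal criteria are tied to mood, and Aim 2 hypothesizes that creatine improves mood. If it does, women on creatine may stay longer and give more samples. Conversely, the Risks and Benefits section names gastrointestinal discomfort from study medication, which could lower retention on creatine. Either way, a retention difference could be reported as a difference in MA use.

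**Working it through.** **The plan's own figure.** 75 / (1 − 0.20) = 93.75, so 94, against 95 stated. The recruitment target is reproduced to within two women. It rests on one overall attrition rate, with no figure by arm.

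**Inputs from the documents.** Two visits a week for eight weeks give 2 × 8 = 16 possible tests. This is inferred, because Table 2A shows one mark per week; if collection is weekly, 8 tests are due. Two arm sizes are used because the text gives two: 47 on placebo (Study Procedures), and about 61 per arm from 123 randomised 1:1.

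**Assumptions (not in the documents).** The probability p that a test is MA-free is 0.3, 0.5 or 0.7 and is equal in both arms. Dropout d by arm averages 20%. Dropouts leave after a uniformly distributed visit from 0 to 15, a mean of 7.5 tests. Missing a test is unrelated to MA use.

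**Formula.** Mean tests attended = (1 − d) × 16 + d × 7.5. Expected count = p × mean tests attended.

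**Results with 16 tests.**
- 20% in both arms: 0.80 × 16 + 0.20 × 7.5 = 14.30 in each, so the gap is 0.
- 15% vs 25%: 14.725 vs 13.875, a difference of 0.85 tests attended. The gap in the count is 0.26 (p = 0.3), 0.43 (p = 0.5) or 0.60 (p = 0.7).
- 10% vs 30%: 14.40 + 0.75 = 15.15 vs 11.20 + 2.25 = 13.45, a difference of 1.70. Counts are 4.55 vs 4.04 (gap 0.51), 7.58 vs 6.73 (gap 0.85) and 10.61 vs 9.42 (gap 1.19).

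The simpler approximation 16 × (1 − d/2) × p, at p = 0.5, gives much the same: 7.4 vs 7.0 for 15% vs 25%, and 7.6 vs 6.8 for 10% vs 30%.

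**Results with 8 tests, 10% vs 30%.** 0.90 × 8 + 0.10 × 3.5 = 7.55 vs 0.70 × 8 + 0.30 × 3.5 = 6.65, a difference of 0.90. The gap is 0.27, 0.45 or 0.63.

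**False-positive rate (simulation).** Beta-binomial tests with within-woman correlation 0.3 or 0.5, the same p in both arms, 16 tests, and a t-test on the count at two-sided 0.05:

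| Dropout | 47 per arm | 61 per arm |
|---|---|---|
| 20% vs 20% | about 5% | about 5% |
| 10% vs 30% | 7–21% | 8–27% |
| 10% vs 30%, with attendance while enrolled 90% vs 80% | 15–61% | 19–74% |

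At 15% vs 25% the rate is roughly 5–11% across both arm sizes. The same t-test on the proportion of attended tests stays at 4–6% in every scenario with the same p, with a mean arm difference of 0.00. That holds only because missingness was simulated as unrelated to use.

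**Scheduled tests as denominator.** Count / 16 is the count rescaled: same ranking, same group comparison. A missed-as-positive analysis is therefore the raw count in another unit.

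**The case against.** The strongest objection is that the protocol states a question, not an estimator. No score, test or model is named, and a per-test analysis is compatible with the wording. That stands: the defect is under-specification. A reader might infer that the sponsor has committed to a biased analysis, but the documents do not go that far.

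A reader might also infer that the bias favours creatine. That needs better retention on creatine. The documents give only 20% overall, and tolerability could reverse the sign. The mood route is also weaker than Table 1 alone suggests, because the HAMD criterion is missing from the early-termination list under Trial Stopping Rules. Psychiatric hospitalization and suicide attempt are in both lists.

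Counting missed tests as not MA-free can be a deliberate conservative choice. Some exits, such as incarceration or non-compliance, may go with use, and then the count may be nearer the truth than the attended-test percentage. This also stands, but the plan does not state that choice.

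Finally, the size is modest in the milder scenario, and no document supports a threefold dropout difference. That is fair: the 10% vs 30% figures are an illustration, not a forecast.

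**Conclusion.** The point holds as a gap in an exploratory outcome. Taken as written, the comparison cannot separate MA use from retention. With equal retention and attendance there is no distortion. At an assumed 10% vs 30% dropout, the arm with better retention gains about 0.5 to 1.2 tests out of 16, or about 0.3 to 0.6 out of 8, with no difference in the chance of an MA-free test. These sizes rest on assumed dropout by arm, assumed MA-free rates, and missingness unrelated to use. The sign is not fixed by the documents.

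It would be wrong to infer that the trial's main conclusions are at risk: the comparison lies outside Aims 1 to 3. It is nevertheless the only stated between-arm comparison of MA use, so its reading should be settled beforehand.

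**What to change.** State whether urine is collected at one or both weekly visits, and so how many tests are due. Then:

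- Analyse each scheduled test as MA-positive or MA-negative by arm with a binomial (logit) GEE, extending the framework already planned, and report the percentage of attended tests that are MA-free.
- Beside it, report the missed-as-positive analysis, labelled as equivalent to the count divided by scheduled tests.
- Report the number of tests attended by arm.
- Interpret a difference as reduced MA use only if the two analyses agree.

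The cost is the wording of one exploratory outcome and a small added table. No visit, sample or participant burden is added. The downside is that neither measure is unbiased on its own. The attended-test GEE relies on missingness being unrelated to use and will mislead if women miss visits when using MA. The missed-as-positive analysis carries the retention problem described here. Both must therefore be shown, and agreement between them is a safeguard, not proof.
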